5.1. Study design:⁸

Our community partners are two federally-qualified health centers (FQHC). FQHC #1 is located in the Tacoma area in Washington and the FQHC #2 is located in the San Fernando/Santa Clarita areas in Los Angeles, CA. FQHC #1 has 4 clinics participating in the study and FQHC #2 has 6 clinics participating in the study. The total number of clinics participating in the study is 10. The cluster randomization was conducted at the end of 2017 by the study statistician. The clinics were placed in blocks by FQHC, location and size and the assignment to control or intervention was done using a computer-generated random allocation. Below are the cluster-randomized assignments, stratified by block and clinic size:

Block	FQHC #1	Assignment
1	Eastside Lakewood	Intervention Control
2	Parkland Spanaway	Control Intervention

Block	FQHC #2	Assignment
1	Canoga Park Van Nuys	Control Intervention
2	Pacoima San Fernando	Intervention Control
3	Santa Clarita Valencia	Intervention Control

The five clinics randomized to intervention will implement the newly adapted model of well child check-up visits for children ages 0-3. The five clinics randomized to control will continue to use the same services that the clinics provide--their usual check-up visit as their typical clinician-led visit (well-visit time slots vary by practice).

Parent/legal guardians will receive the same services offered by these clinics for their child's health care whether they participate in this study or not.

Components of the newly designed model of WCC:

The PARENT intervention was adapted during the Project Working Group meetings in partnership with the two FQHCs (Phase 1: IRB ID: STUDY00000413).

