10.3. Number of screened subjects versus the actual number enrolled in the research:³¹

2 to 1. In other words, we will expect to screen doubled the number of actual people enrolled in the study

10.4. Power analysis:

The power calculation is based on WCC quality (anticipatory guidance) and ED visits (2 or more), with a 1:1 randomization of 10 sites into the intervention and control groups. We use the mean and standard deviation (SD) of anticipatory guidance and the rates of 2 or more ED visits as observed in our pilot RCT. For anticipatory guidance, we use the larger SD from the two groups to have a conservative power estimation for this variable. The calculation assumes an intra-class correlation of 0.01 based on previous delivery systems design cluster RCTs among similar populations^{81, 82} and the fact that the data analysis will be adjusted for important baseline covariates when comparing the intervention versus control groups⁸³. A 20% dropout rate is assumed at the patient level. Two-sided tests are used with a type I error rate of 0.05. With an N of 75 per site, we will have at least 80% power to detect the intervention effect for both anticipatory guidance and ED visits. After accommodating a 20% dropout rate at the patient level, the N per site is 94, or a total sample of 940 participants.

11. Withdrawal of Subjects

11.1. Anticipated circumstances under which subjects will be withdrawn from the research without their consent:

Subjects can choose whether to be in this study or not. If they agree to participate, they may withdraw their consent at any time without impacting their care. For this study, we do not anticipate the need to withdraw subject due to investigator judgement.

11.2. Procedures for orderly termination:

N/A

11.3. Procedures that will be followed when subjects withdraw from the research, including partial withdrawal from procedures with continued data collection and withdrawal from data/specimen banking:

Data collected on any withdrawn subjects will be removed from the analysis

12. Risks to Subjects**12.1. Reasonably foreseeable risks to subjects (include each study population, each arm, and optional procedures):**

There is a risk that confidentiality or privacy could be breached and people could find out if someone was in the study.

12.2. Procedures with unforeseeable risks:

N/A

12.3. Procedures with risks to an embryo or fetus should the subject be or become pregnant:

N/A

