12.4. Risks to others who are not subjects:

N/A

12.5. Procedures performed to lessen the probability or magnitude of risks:

N/A

13. Potential Benefits to Subjects**13.1. Potential benefits that individual subjects may experience from taking part in the research.³²**

We do not anticipate any direct benefit to participating subjects.

14. Data Analysis/Management**14.1. Data analysis plan, including statistical procedures:**

We will compile descriptive statistics on all outcome variables, composite scores, and covariates. We will report means, medians, and standard deviations for continuous variables, create graphical displays to visualize distributions, and transform variables with non-normal distributions. Next, we will use multivariable analyses to examine differences between the control and intervention groups on the measures described above. From these analyses, we will estimate intervention effects. An intent-to-treat approach will be used, that is, parents will be analyzed according to the assigned group regardless of deviations from the study protocol. Sensitivity analysis will be conducted by performing the analyses with and without outliers and influential data points. Missing values will be excluded from the analysis if the missing rate is low (< 10%). If the missing rate is more than 10%, data may also be imputed using multiple imputation techniques and the analysis can then be done based on the complete, imputed datasets. All tests are two-sided, and p values < 0.05 are considered statistically significant.

Specific Aim 1: We will analyze anticipatory guidance based on data collected at 12-months post enrollment. We will assess intervention effect on anticipatory guidance via linear mixed effects models that involve random effects to capture data clustering within clinic, given

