the fact that randomization is done at the clinic level. The outcome may be subject to transformation prior to fitting the model if non-normality is observed. The analysis will include intervention status as the main independent variable, adjusted for baseline covariates and other confounding factors. We will also test possible interaction effects between intervention and these covariates. All other outcome variables to measure experiences of care and receipt of other nationally-recommended WCC services are regarded as secondary. Each outcome will be analyzed using linear or generalized linear mixed effects models depending upon data distributions, with a similar setting as described above for anticipatory guidance.

Specific Aim 2a: Intervention effects on healthcare utilization (ER visits, hospitalizations, urgent care visits, regional center/early intervention, maternal mental health, support groups (e.g., breastfeeding, parenting classes), dentist, case management/social services) will be assessed using generalized linear mixed effects models for binary or count data with a similar setup as outlined for Aim 1. The model will include random effects to capture data clustering within clinic and the primary independent variable is intervention status. The analysis will be adjusted for any baseline child, parent, or household characteristics that are significantly different between control and intervention groups. We will also test interaction effects between intervention and the covariates.

Specific Aim 2b: Cost/cost-offset Analysis. We will conduct our analysis from the perspectives of the “social planner”⁸⁰ and of the payer (e.g., health plan or medical group), and consider intervention costs (direct and indirect) and cost offsets.

Specific Aim 4: We will utilize the same approach as described for Specific Aims 1 and 2a; i.e., linear or generalized linear mixed effects models, depending on the distribution of the outcome variables.

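### Section 14.1 names no estimator, reference distribution or degrees of freedom for mixed-model tests on 10 clinics; if Wald z is used at the plan's ICC of 0.01, linear-model type I error is about 7% (REML) to 9% (ML), not 5%

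*Combined protocol and SAP*

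**What the plan says.** **Design (5.1).** Ten clinics, five per arm, were randomized in five blocks of two: "The clinics were placed in blocks by FQHC, location and size".

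**Error rate and power (10.4).** "Two-sided tests are used with a type I error rate of 0.05". The ICC is taken as 0.01, partly because "the data analysis will be adjusted for important baseline covariates when comparing the intervention versus control groups". "With an N of 75 per site, we will have at least 80% power to detect the intervention effect", for anticipatory guidance and for two or more ED visits. The pilot means, SD and rates behind that statement are not given.

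**Analysis (14.1).** Anticipatory guidance is tested "via linear mixed effects models that involve random effects to capture data clustering within clinic". Utilization outcomes, including ER visits, "will be assessed using generalized linear mixed effects models for binary or count data with a similar setup as outlined for Aim 1". For Aim 4, "We will utilize the same approach as described for Specific Aims 1 and 2a". The decision rule is common to all: "All tests are two-sided, and p values < 0.05 are considered statistically significant".

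**Not stated.** Neither section says whether the models are fitted by REML or ML, whether the arm effect is referred to a normal or a t distribution, what the degrees of freedom are, or whether a small-sample correction or clinic-level test applies. Section 14.1 also does not say whether FQHC or the five randomization pairs are in the model.

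**The concern.** The arm effect is a between-clinic contrast. Its standard error rests on the variation among ten clinics, so at most 8 degrees of freedom support it, however many families are enrolled. A Wald z test treats that standard error as known. The plan neither requires nor excludes such a test.

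If z is used, the 5% in 10.4 is not held and nominal 95% intervals cover about 91-93% for the linear model at the plan's ICC. If a t reference on between-clinic df is used with REML, the error rate is held and only the documentation is lacking. The open choices are REML or ML, z or t, and 8, 7 or 4 df (no design term, FQHC fitted, pairs fitted). They affect both outcomes that drive the sample size, and nothing in the documents prevents them from being settled after the data are seen.

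**Working it through.** **Inputs from the documents.** 5 versus 5 clinics (5.1); ICC 0.01, 75 analysed per clinic, two-sided 0.05, power of at least 80%, 20% dropout (10.4).

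**The plan's own figure.** 75 / 0.80 = 93.75, rounded up to 94; 94 × 10 = 940, as in 10.4. The step from 75 per clinic to 80% power cannot be reproduced without the pilot values.

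**Standard error.** With total variance 1, a clinic mean has variance 0.01 + 0.99/75 = 0.0232, which is the design effect 1 + 74 × 0.01 = 1.74 divided by 75. The arm difference has SE √(2 × 0.0232/5) = 0.0963.

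**Analytic limit for Wald z, 8 df.** When the clinic variance is not estimated as zero, the REML statistic follows t on 8 df and the ML variance is smaller by a factor of 8/10.
- REML: 2 × P(t₈ > 1.960) = 8.6%.
- ML: 2 × P(t₈ > 1.960 × √0.8) = 2 × P(t₈ > 1.753) = 11.8%.

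At ICC 0.01, REML estimates the clinic variance as zero in 19.6% of trials. It then uses the pooled variance, which pulls the rates below these limits.

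**Null simulation, balanced linear model, 75 per clinic, no FQHC or pair term** (1,000,000 runs per case):

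| ICC | Wald z, REML | Wald z, ML |
|---|---|---|
| 0 | 3.9% | 4.5% |
| 0.001 | 4.4% | 5.1% |
| 0.005 | 5.9% | 7.2% |
| **0.01 (plan)** | **7.0%** | **8.9%** |
| 0.02 | 8.0% | 10.6% |
| 0.05 | 8.5% | 11.6% |

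At ICC 0.01 a clinic-level t gives 5.0%. A Kenward-Roger-type reference (8 df, or residual df when the clinic variance is zero) gives 4.7%.

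**Variations at ICC 0.01, Wald z (REML / ML).**
- Individual-level covariate (assumed R² 0.2), equal clinics: 7.0% / 8.9%.
- The same with assumed sizes of 50-100 per clinic: 7.0% / 9.1%.
- FQHC fitted (7 df): 7.1% / 10.0%.
- Pairs fitted (4 df): 7.7% / 12.9% if pairing removes no between-clinic variance, 6.1% / 9.2% if half, 3.8% / 5.0% if all.

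**Logistic model, 10,000-20,000 runs, assumed ED rates of 10, 15 and 20%.** Wald z rejects 8.4-8.8% if the ICC of 0.01 is on the proportion scale and 5.7-7.4% if on the logit scale. A t on 8 df applied to the mixed-model estimate is conservative (2.6-4.7%). A two-stage clinic-level t gives 4.8-5.4%. Count models were not simulated.

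**Power, conditional only.** Exactly 80% on a normal reference means a noncentrality of 1.960 + 0.842 = 2.80. The noncentral t on 8 df (critical value 2.306) then gives 69%. For 80% on 8 df the noncentrality must be 3.201, which is normal-theory power Φ(3.201 − 1.960) = 89%.

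**The case against.** The strongest reply is that this is an omission, not an error. Section 14.1 picks the right model class and justifies it by the unit of randomization. No passage commits to z, and the documents cannot show which reference the analyst's software would apply. That stands. A reader might infer that the trial will have a 7-9% false-positive rate; the documents do not support this, because the figure is conditional on a z reference.

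The range is also local. It needs an ICC near 0.01 and no FQHC or pair term, and its upper end needs ML as well as z. With REML at ICC 0.005 the excess is under one point, and at 0.001 or below there is none. But 0.01 is the plan's own value, and larger values make the problem worse. Covariate adjustment does not remove it, because individual-level covariates add no clinics.

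The non-linear part is weaker: the logistic figures rest on ED rates and an ICC scale that are not in the documents, and their lower end is slight. Aim 4 is labelled exploratory, so strict error control matters less there.

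A reader might also infer that the power claim in 10.4 is wrong. The documents do not show this. The claim is at least 80%, one N serves two endpoints, the larger pilot SD was used for anticipatory guidance, and 100 rather than 94 per clinic are to be enrolled.

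**Conclusion.** The omission is certain: ten clusters are tested at p < 0.05 with estimator, reference distribution and df all unstated. The linear-model consequence is well established but conditional. If Wald z is used at ICC 0.01 and 75 per clinic without FQHC or pair terms, type I error is about 7% (REML) to 9% (ML) against the stated 5%. It lies between about 4% and 13% across the REML/ML and design-term choices examined at that ICC, the low end arising only if pairing removes all between-clinic variance. For logistic models about 6-9% is indicative, resting on assumed ED rates of 10-20% and the ICC scale. Nothing is claimed numerically for count models.

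On power, exactly 80% on a normal reference would be about 69% on 8 df, while normal-theory power of 89% or more would leave at least 80%. Which case applies cannot be told from the documents. The plan should be amended; this is not evidence that the design has failed.

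**What to change.** **In 14.1:**
- For linear outcomes, specify REML with Kenward-Roger (or Satterthwaite) df. REML needs naming too: an ML fit with t on 8 df still rejects about 6.2% at ICC 0.02.
- For binary and count outcomes, specify a two-stage clinic-level t analysis, or a t reference on between-clinic df. In the logistic runs the former stayed near 5% and the latter was conservative.
- State before analysis one choice on design terms with its df: neither (8), FQHC (7) or the five pairs (4).
- Do not rely on a within-pair permutation test. Five pairs give 2⁵ = 32 allocations, so the smallest two-sided p is 2/32 = 0.0625.

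**In 10.4:** confirm that the stated power uses the same reference, and restate it if not.

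**Cost.** Wording only, with no added participants. At the same standard error, intervals widen by 2.306/1.960, about 18%, on 8 df; 2.365/1.960, about 21%, on 7 df; and 2.776/1.960, about 42%, on 4 df. These are upper figures: with a Kenward-Roger-type rule that reverts to residual df when the clinic variance is zero, the average at ICC 0.01 is about 15%, 17% and 32%. Fitting pairs recovers some of this if pairing removes clinic variance. The stated power may become less favourable if 10.4 used a normal reference with little slack, and wording alone would not restore it.

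### Section 14.1 tests intervention-by-covariate interactions at unadjusted p < 0.05 with no fixed list of modifiers, and in Aim 2a baseline imbalance picks the modifiers

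*Combined protocol and SAP*

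**What the plan says.** All of this is in section 14.1 (Data analysis plan).

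- **Aim 1.** The model for anticipatory guidance is "adjusted for baseline covariates and other confounding factors"; none is named. Then: "We will also test possible interaction effects between intervention and these covariates".
- **Aim 2a.** The utilization models are "adjusted for any baseline child, parent, or household characteristics that are significantly different between control and intervention groups". Then: "We will also test interaction effects between intervention and the covariates".
- **Random effects.** Aim 1 uses "linear mixed effects models that involve random effects to capture data clustering within clinic". Aim 2a says "The model will include random effects to capture data clustering within clinic". Neither says whether these are intercepts alone or also covariate slopes, and no degrees-of-freedom method is given.
- **Significance rule.** "All tests are two-sided, and p values < 0.05 are considered statistically significant".

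The documents give no list or count of modifiers, no multiplicity control and no rule for acting on a significant interaction. Aim 4 is described as exploratory; the interaction tests in Aims 1 and 2a are not.

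**The concern.** There are three linked problems.

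1. An open set of interaction tests, each judged at 0.05, will often produce at least one significant result by chance. Under the plan's own rule, that result counts as statistically significant.
2. In Aim 2a the covariates are those that happen to be imbalanced between arms, so the list of modifiers is a product of chance. Natural candidates such as FQHC or parent language might never be examined, although the trial spans two FQHCs in two states and enrols English- and Spanish-speaking families.
3. Allocation is by clinic, five clinics per arm. An interaction between arm and a patient covariate compares covariate slopes between two sets of five clinics. If the model allows clinics to differ in level but not in slope, real slope variation is left out of the standard error and the test rejects too often.

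At stake is the credibility of any statement that PARENT works better in one kind of family than another, should such a statement be used to guide roll-out.

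**Working it through.** **Inputs from the documents**
- Section 10.4: 10 clinics allocated 1:1, 75 analysable per clinic, ICC 0.01, two-sided alpha 0.05.
- Section 14.1: anticipatory guidance plus eight listed utilization categories, so nine countable outcomes. The other Aim 1 outcomes and those of Aim 4 are not counted here.

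**Assumed, because the documents do not say:** the number of covariates, the between-clinic SD of a covariate's slope, and the prevalence of a binary covariate (50%).

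**The plan's own figure.** 75 / (1 − 0.20) = 93.75, rounded up to 94 per clinic; 94 × 10 = 940. This matches section 10.4 and confirms 75 as the analysable number. The plan states no error rate for the interaction tests beyond p < 0.05.

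**Multiplicity.** With k independent tests and all nulls true, P(at least one false positive) = 1 − 0.95^k, and the expected number of false positives is 0.05k.

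| Scenario | k | P(at least one) | Expected |
|---|---|---|---|
| Guidance only, 6 covariates | 6 | 26% | 0.3 |
| Guidance only, 10 covariates | 10 | 40% | 0.5 |
| Guidance 6–10, Aim 2a 1 covariate | 14–18 | 51–60% | 0.7–0.9 |
| Guidance 6–10, Aim 2a 2 covariates | 22–26 | 68–74% | 1.1–1.3 |
| Nine outcomes, 3 covariates | 27 | 75% | 1.35 |
| Nine outcomes, 6 covariates | 54 | 94% | 2.7 |
| Nine outcomes, 10 covariates | 90 | 99% | 4.5 |

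Reaching 95% takes 59 independent tests, which is seven or more covariates on all nine outcomes. With a correlation of 0.3 among outcomes and among covariates, the nine-outcome figures for 3, 6 and 10 covariates fall to 68%, 88% and 96%. With a correlation of 0.5 they fall to 56%, 76% and 88%.

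**Size of a single test if only random intercepts are fitted.** Take a continuous outcome with residual variance about 1, m patients per clinic, covariate variance v, and slope variance τ² between clinics. The true variance of the interaction estimate exceeds the model's by the ratio R = 1 + mτ²v. The actual size is 2[1 − Φ(1.96/√R)]. With m = 75 and v = 0.5 × 0.5 = 0.25:

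| Slope SD τ (patient SD units) | R | Size |
|---|---|---|
| 0 | 1.000 | 5.0% |
| 0.05 | 1.047 | 5.5% |
| 0.10 | 1.188 | 7.2% |
| 0.15 | 1.422 | 10.0% |
| 0.20 | 1.750 | 13.8% |

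Simulation of 4,000 trials (5 v 5 clinics of 75, ICC 0.01, no true interaction) gave 4.7%, 6.9%, 10.3% and 13.8% at τ = 0, 0.10, 0.15 and 0.20. A t test on the ten clinic-specific slopes (8 df) gave 4.7–5.0% throughout.

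**A clinic-level modifier.** For FQHC (4 v 6 clinics), a simulated Wald z test of the interaction ran at about 8–11% for ICC 0.01–0.05. With t on 6 df it ran at about 4–5%.

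**Clinic-specific slopes for ED visits.** Assume an event rate of 5–10% and about 37 patients per clinic and covariate level, giving 20 cells. The chance that at least one cell has no events is 1 − (1 − 0.95^37)^20 = 96% at 5%, and 1 − (1 − 0.90^37)^20 = 34% at 10%. Separate clinic slopes may therefore not be estimable for this outcome.

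**The case against.** Much of the case against a stronger reading stands.

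- **That false interactions are near certain.** A reader might infer this, but it needs a covariate count that the documents do not give. It also fits poorly with Aim 2a, where only imbalanced characteristics enter and there may be few or none; clustering could raise that number. Outcomes from the same families are probably correlated, which lowers the figure. Aim 1 speaks only of possible interactions. Carrying the tests over to the other Aim 1 outcomes and to Aim 4 is an inference from general wording about using a similar model.
- **That the models contain random intercepts only.** The text neither specifies nor excludes slopes, so this treats silence as exclusion.
- **That a single test runs at 7–14%.** This follows from assumed slope SDs of 0.10–0.20. The planned ICC of 0.01 implies a between-clinic SD of about √0.01 = 0.10 for outcome levels, so the 14% case needs slopes to vary with twice that SD. Nothing in the documents supports that. The calculation is also for a continuous outcome, whereas the eight utilization categories are to be modelled as binary or count data.
- **That most subgroup statements would be chance.** This presumes that nearly all nulls are true and that such statements would be made; the plan commits to none.

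What remains is explicit in the text: interaction tests on an unlisted set of covariates, unadjusted at 0.05, with the Aim 2a modifiers selected by baseline imbalance.

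**Conclusion.** The point holds as a minor but real weakness in the plan for effect modification. The selection rule and the 0.05 threshold are stated, not inferred. How much error follows depends on covariate counts that the documents leave open: about 26–40% for at least one false interaction if only anticipatory guidance is tested with 6–10 covariates, and 75–99% with 3–10 covariates on all nine countable outcomes. Both ranges assume independent tests and no true interactions, and correlation lowers them.

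The excess size of a single test is conditional on two things the plan does not settle: random intercepts without slopes, and slopes that truly differ between clinics. Under both, and for a continuous outcome with a 50% prevalent covariate and 75 per clinic, it is about 5.5%, 7%, 10% and 14% at slope SD 0.05, 0.10, 0.15 and 0.20; if slopes do not vary it is 5%. The documents therefore do not support calling false claims near certain, or giving 7–14% as the test's actual error rate. The analyses of the main treatment effect are untouched.

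**What to change.** Replace both interaction sentences in section 14.1 with the following:

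- A short list of modifiers, fixed before any unblinded analysis and not chosen by baseline imbalance. FQHC, parent language and infant age at enrolment are examples; the choice is the investigators'.
- Interaction analyses limited to anticipatory guidance and ED visits, the two outcomes in the power calculation.
- Reporting as exploratory, with confidence intervals and no significance claims.
- A stated method for each case:
  - Patient-level modifiers of anticipatory guidance: compare the ten clinic-specific slopes between arms on 8 df, or fit a clinic random slope with small-sample degrees of freedom. The 8-df comparison held its size in simulation; the random-slope option was not simulated.
  - FQHC: a clinic-level test with t on about 6 df.
  - ED visits: a model-based random slope rather than separate clinic slopes if cells are sparse.

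The change is SAP wording and needs no extra participants or data. The price is fewer subgroup analyses and wider intervals for the interactions.

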2.2. Relevant preliminary data:¹

This application is the next phase of a previously approved application (IRB ID: STUDY00000413)

2.3. Scientific or scholarly background:

A pilot randomized controlled trial (RCT) (n=251) of the PARENT intervention in 2 clinics demonstrated robust improvements in parent- reported receipt of WCC services (e.g., psychosocial screening, health education and guidance, and developmental screening, surveillance), experiences of care, and reduced emergency department (ED) visit.

2.4. Prior approvals:

None

3. Study Endpoints²

3.1. Primary and secondary endpoints:

Improvement of WCC services (e.g., psychosocial screening, health education and guidance, and developmental screening, surveillance).

Improvement of parent experiences of care

Reduction in emergency department (ED) visits

3.2. Primary or secondary safety endpoints:

This study has minimal risk to participants. There are no safety endpoints.

4. Drugs, Devices and Biologics³

4.1. Manufacturer and name of all drugs, devices and biologics:

N/A

4.2. Description and purpose of all drugs, devices and biologics:

N/A

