We will collect information on the number of people approached, the number of people who agreed to participate and the number of people who refused to participate and the reasons for their refusal.

We will collect contact information from the enrolled parent/legal guardian and spouse/partner (home and cell phone, email) to telephone them to complete the baseline survey, if needed. The information will be verified at each subsequent contact for the follow up surveys at 6-month and 12-months from date of enrollment. We will also ask parents to provide contact information for three relatives/friends who will always know their whereabouts. Because this study population frequently changes phone numbers, we will also ask participants to provide any social media handles, if they are willing, so that the study team can direct message them. Direct messaging will be utilized to get updated phone numbers or schedule a phone conversation and no other purposes. Additionally, to support retention we will contact participants by cell phone and email at 3- and 9-month time points to remind them of their study participation as well as confirm their contact information has not changed. Furthermore, we will send participating families a card for their baby's first birthday and for New Years from the research team to encourage engagement, remind them of their participation, and support follow-up survey retention.

The research staff will ask parents/legal guardians questions about their experiences in getting care so that we can compare the two types of well-child care.

We will conduct three waves of survey data (baseline, 6-month and 12-month) collection and chart review at the end:

- Baseline Survey (at enrollment): Experienced research staff will be responsible for data collection. Upon enrollment, parents will participate in a 35-minute survey to collect baseline demographic data on the infant, parent, and household and child's medical history.

- 6-Month Survey (participant retention survey by phone): Research staff will conduct a 15-minute phone survey at 6-months post-enrollment to aid in participant retention. The 6-month survey will update the child's medical history, household changes, and healthcare utilization (e.g., ED utilization).

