- 12-month Survey: At 12-months post-enrollment, all participants will be asked to complete a 40-minute survey by phone. This survey administration will include the Promoting Healthy Development Survey (PHDS-PLUS), a parent survey that assesses the provision of nationally recommended WCC services. We will use the PHDS-PLUS to determine parent perceived receipt of recommended WCC services, appropriate follow-up, and health care utilization. Additional questions on social determinants screening and referral are included and drawn from the PHDS-PLUS as well as the National Survey of Early Childhood Health. We will also use items on overall satisfaction of care from the Consumer Assessment of Healthcare Providers and Systems (CAHPS) Health Plan Survey and family-centeredness of care from the National Survey of Children's Health. Using previously validated parent survey tools, we will collect data on our exploratory measures of parental mental health, perceived parenting self-efficacy and parenting behaviors.
For the 6-month and 12 month follow up surveys, we will contact study participants two weeks before the due date. If we are unable to reach them by the due date, we will continue calling them up to three months after the due date to complete the survey.
- Chart review: After completing the three waves of survey data collection, we will conduct chart review. The chart review includes clinic visits, ED visits, services received at those visits, immunizations, and status of referrals.

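### Does Aim 2a need to restate the two-or-more coding of ED visits and name survey or chart as the source?

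*Combined protocol and SAP*

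**What the plan says.** Section 3.1 lists the endpoint simply as "Reduction in emergency department (ED) visits", with no threshold and no source. Section 10.4 is more specific: "The power calculation is based on WCC quality (anticipatory guidance) and ED visits (2 or more"). It takes the rates from the pilot trial, and adds "A 20% dropout rate is assumed at the patient level".

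In section 14.1, Specific Aim 1 fixes the data for the other sizing outcome: "We will analyze anticipatory guidance based on data collected at 12-months post enrollment". Specific Aim 2a puts ED visits first in a list of eight kinds of utilization, which "will be assessed using generalized linear mixed effects models for binary or count data". On missing data, 14.1 drops missing values when fewer than 10% are missing, and otherwise says: "If the missing rate is more than 10%, data may also be imputed using multiple imputation techniques".

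Section 5.2 collects ED use in more than one way. The 6-month phone survey updates "household changes, and healthcare utilization (e.g., ED utilization"). For the 12-month survey: "We will use the PHDS-PLUS to determine parent perceived receipt of recommended WCC services, appropriate follow-up, and health care utilization". The chart review at the end also lists ED visits. Section 5.3 names surveys and charts as sources without assigning either to an outcome.

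**The concern.** The trial is sized on two outcomes. For one of them the analysis section states the model and the data. For the other, a reader has to take the coding from the power section and infer the source. Aim 2a would equally permit a count model.

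The source could decide who is analysed. A family lost to the surveys has no parent-reported ED outcome, but might still have a chart. At the assumed dropout a survey outcome passes the 10% limit, so imputation comes into play; a chart outcome might not reach it. If coding and source were both left open until results were seen, the most favourable combination could be reported, and the 5% error rate would no longer hold. Readers might also not know which result the 80% power refers to.

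**Working it through.** **The plan's own figure.** Section 10.4 needs 75 followed families per clinic. With 20% dropout, 75 / (1 − 0.20) = 93.75, rounded up to 94 per clinic; 94 × 10 = 940. This reproduces the stated total. The claim of at least 80% power cannot be reproduced, because the pilot mean, SD and ED rates are not given.

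**Families in each analysis.** The 940 is the requirement. Sections 2.1 and 10.2 plan to enroll 100 × 10 = 1,000.

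- Survey outcome: 1,000 × 0.80 = 800.
- Chart outcome: at most 1,000. Section 11.3 removes the data of withdrawn families, so the true ceiling is lower by an unknown number.
- Largest difference: 200 families, against 940 − 750 = 190 on the 10.4 numbers.

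**What that does to power.** Inputs from 10.4: intra-class correlation 0.01, five clinics per arm, two-sided 5%. For m families per clinic, the design effect is 1 + (m − 1) × 0.01 and the effective number per arm is 5m divided by it. As a stand-in for the mixed model, use a t-test on clinic means with 8 degrees of freedom. Power of 80% then needs a noncentrality of 3.20. Assume that 10.4 gives exactly 80% at m = 75. For the same effect the noncentrality grows with the square root of the effective number, so the unknown ED rates drop out.

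| m per clinic | Design effect | Effective n per arm | Noncentrality | Power |
|---|---|---|---|---|
| 75 (10.4, followed) | 1.74 | 375 / 1.74 = 215.5 | 3.20 | 80% |
| 80 (planned, followed) | 1.79 | 400 / 1.79 = 223.5 | 3.26 | 81% |
| 94 (10.4, enrolled) | 1.93 | 470 / 1.93 = 243.5 | 3.40 | 84% |
| 100 (planned, enrolled) | 1.99 | 500 / 1.99 = 251.3 | 3.46 | 86% |

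On numbers alone, either source keeps the power that 10.4 asks for.

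**Coding.** A two-or-more outcome is binary, and Aim 2a covers binary data. The two sections agree.

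**Source.** Three features point to the surveys.

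1. Section 5.2 gives the 12-month survey the task of determining health care utilization, and Aim 2a is the utilization aim.
2. Section 10.4 applies the same 75 per clinic after dropout to both sizing outcomes, so ED visits were sized as an outcome lost when a family drops out.
3. Several items in the Aim 2a list, such as support groups, dentist and maternal mental health, are not named among the chart-review items, although referral status in the chart may touch some of them.

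Against this, ED visits are named under chart review. The balance favours the surveys but does not prove it.

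**Missing data.** Section 14.1 has one rule with a 10% threshold. A survey and a chart outcome could fall on different sides of it, but the rule is the same.

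**The case for a change.** The best case for a change is that a sample-size section does not govern the test. Section 14.1 does, and it admits a count. The survey sentence in 5.2 concerns the 12-month instrument and does not say how 6-month reports are used. The same section places ED visits in the chart review, and nothing ranks the two. A sentence or two would close the gap.

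The risk from leaving everything open can be illustrated. In simulations with no true effect, reporting the better of survey and chart for two or more visits gave 6.0 to 8.8% false positives. The best of two codings and two sources gave 8.3 to 12.4%. Single tests stayed at 4.5 to 5.3%. These figures assume control rates of 10 to 30%, Poisson or negative binomial counts, and capture of 90 to 100% of visits by survey and 60 to 90% by chart; the documents give none of these. They also require running several tests and reporting the best, which the plan nowhere proposes.

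What stands is that the source is not ranked and that Aim 2a does not point back to 10.4. It does not stand that one answer is plainly right. Parent report carries recall error, and parents know which model of care they received. The documents do not say whether clinic charts hold ED visits made elsewhere. Combining the two surveys could count visits twice, because no recall period is given for the 12-month survey. Section 5.3 says the survey and data collection forms are attached separately, and they may settle this.

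**Conclusion.** No change to the plan is needed. This is missing detail in Aim 2a, not a contradiction or an error of calculation. The coding appears in 10.4 and fits the models allowed in 14.1. The source is left to inference, with the text leaning towards the surveys. The choice affects at most about 200 of 1,000 planned families. On sample size alone it moves power between about 81% and 86%, both above the 80% target.

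Those figures assume exactly 80% power at 75 per clinic, the stated intra-class correlation and dropout, an approximate clinic-level test, and complete charts for everyone enrolled. They say nothing about how accurately each source records visits, which the documents do not address. The conclusion also assumes that the team settles coding and source before ED data are analysed. An analyst would ordinarily carry the 10.4 coding forward, take one source as the main one and use the other as a check.
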